7.5. Exploratory Efficacy Endpoints and Analyses

7.5.1. Overall Survival

Overall survival is defined as time from randomization to date of death prior to data cut-off date. The Kaplan-Meier method will be used to describe survival distributions by treatment group. Patients will be censored at the last contact date prior to data cut-off date if patient is known to be alive prior to data cut-off date.

7.5.2. Pharmacogenomics Analyses

A separate SAP may be provided for pharmacogenomic analysis on the presence of polymorphisms in germline genes related to the hypothalamic-pituitary androgen pathway, prostate cancer risk, or to drug-metabolizing enzymes and transporter proteins that might be implicated in the drug disposition, safety, or efficacy of relugolix.

7.6. Patient Reported Outcomes

Patient reported outcome questionnaires (EORTC QLQ-C30, EORTC QLQ-PR25, and EuroQoL EQ-5D-5L) are completed by patients at Day 1, Week 5, Week 13, Week 25, Week 37, Week 49, and the 30-day safety follow-up visit. They are also completed in the 60-day and 90-day testosterone recovery follow up if patients are participating in the testosterone recovery follow up.

7.6.1. EORTC QLQ-C30 and QLQ-PR25

The scoring procedure for EORTC QLQ-C30 and QLQ-PR25 is shown in [Table 6](#):

Table 6: Scoring Procedure

Domain	Number of Items	Item Range ^a	Item Numbers
EORTC QLQ-C30			
Global Health Status	2	6	29, 30
Functional Scales			
Physical functioning	5	3	1 to 5
Role functioning	2	3	6, 7

Emotional functioning	4	3	21 to 24
Cognitive functioning	2	3	20, 25
Social functioning	2	3	26, 27
Symptom Scales			
Fatigue	3	3	10, 12, 18
Nausea and vomiting	2	3	14, 15
Pain	2	3	9, 19
Dyspnoea	1	3	8
Insomnia	1	3	11
Appetite loss	1	3	13
Constipation	1	3	16
Diarrhoea	1	3	17
Financial difficulties	1	3	28
EORTC QLQ-PR25			
Symptom Scales			
Urinary symptoms	8	3	31 to 37, 39
Incontinence aid use	1	3	38
Bowel symptoms	4	3	40 to 43
Hormonal treatment-related symptoms	6	3	44 to 49
Functional Scales			
Sexual activity	2	3	50, 51
Sexual functioning	4	3	52 to 55

^a Item range is the difference between the possible maximum and the minimum response to individual items (eg, range for items taking values from 1 to 4 is 3).

For all scales, the raw score is the average of component items:

$$\text{RawScore} = (I_1 + I_2 + \dots + I_n)/n,$$

Where n is the number of responded items within the scale.

Missing Items

For multi-item scales, if at least half of the items from the scale have been answered, use all the items that were completed and apply the above raw score calculation. Otherwise, set the scale score to missing. For single-item scales, set the score to missing if the response of the item is missing.

Transformation of Scale Scores

Apply the below linear transformation to 0 – 100 to obtain the score:

Functional Scales:

$$\text{Score} = \left\{ 1 - \frac{\text{RawScore}-1}{\text{range}} \right\} \times 100$$

Symptom Scales/Global Health Status:

$$\text{Score} = \left\{ \frac{\text{RawScore}-1}{\text{range}} \right\} \times 100$$

A high scale score represents a higher response level. For example, a high score for a functional scale represents a high/healthy level of functioning while a high score for a symptom scale represents a high level of symptomatology/problems.

Analyses on Scale Scores

Scores and change from baseline scores from each scale will be summarized by each visit and treatment group.

For each scale, a mixed model using repeated measures will be performed with baseline scores, treatment, visit, randomization stratification factors (per EDC if the discrepancy between IWRS and CRF is > 5%), and treatment by visit interaction included as fixed effects. Change from baseline in each scale for each patient at each visit will be included as the dependent variable. An unstructured covariance matrix will be used in the mixed effect model. The least square means from the mixed model using repeated measures will be provided for each treatment group at each visit.

7.6.2. EuroQoL EQ-5D-5L

The EQ-5D-5L consists of the EQ-5D-5L descriptive system and the EQ Visual Analogue Scale (EQ VAS).

The descriptive system comprises 5 dimensions (mobility, self-care, usual activities, pain/discomfort, and anxiety/depression). Each dimension has 5 levels: no problems (1 as numerical score), slight problems (2 as numerical score), moderate problems (3 as numerical score), severe problems (4 as numerical score), and extreme problems (5 as numerical score). There should be only ONE response for each dimension. If more than one box is ticked for a single dimension, it should be treated as missing values. For each dimension, the count and proportion of improvement by level or at least one level will be tabulated by treatment group and each visit. The denominator for the proportion will be based on the number of patients who provided non-missing responses to the dimensions at baseline.

The EQ VAS records the patient's self-rated health on a 20-cm vertical visual analogue scale. It asks respondents to "mark an X on the scale to indicate how your health is TODAY" and then to "write the number you marked on the scale in the box below." If there is a discrepancy between where the respondent has placed the X and the number respondent has written in the box, administrator should use the number in the box. The non-missing EQ VAS score will be summarized, including 25th and 75th percentiles, at each visit by treatment group.

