2.2. Sample Size Justification

The following assumptions were used to determine the sample size for this study:

- True probabilities of sustained testosterone suppression are 94% and 96% for relugolix and leuprolide acetate, respectively;
- 2:1 randomization ratio (relugolix: leuprolide acetate);
- Dropout rate: 15%.

For Evaluation Criterion 1, 610 patients in the relugolix group will provide approximately 90% power to rule out a fixed probability of sustained testosterone suppression of < 90% at a two-sided type I error rate of 0.05.

For Evaluation Criterion 2, with a noninferiority margin of -10% and an overall two-sided type I error rate of 0.05, a total of approximately 915 patients (610 receiving relugolix, 305 receiving leuprolide acetate) will yield at least 99% power to declare the noninferiority of relugolix to leuprolide acetate. The 10% noninferiority margin for the comparison of relugolix versus

leuprorelin is based on regulatory precedence of pivotal assessment of gonadotropin-releasing hormone (GnRH) antagonist degarelix versus leuprorelin as well as studies of branded GnRH agonist generics.

The primary analysis will be performed separately for each evaluation criterion using data collected through 48 weeks after enrollment of approximately 915 patients.

Approximately 915 patients will be randomized in order to fulfill the regulatory requirements of all participating countries included in the primary efficacy endpoint of this study.

Under amendment 3 the study is also powered for the secondary endpoint of castration resistance free survival in the high-risk subgroup of patients with metastatic disease, although this is not part of the primary analysis. Approximately 107 confirmed castration-resistance events (ie, PSA progression while castrated or deaths due to any reasons) will need to be observed (or approximately 390 patients with metastatic disease will need to be enrolled) to detect a hazard ratio of 0.55 (relugolix vs. leuprolide acetate) with 85% power and a two-sided type I error of 5%, assuming a castration-resistant event-free rate of 60% at 48 weeks for the control arm, an 18-month enrollment period, 12 months of additional follow-up, and a 15% dropout rate.

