- For by-visit observed data analyses, calculation of percentages will be calculated on the basis of the number of patients with non-missing data as the denominator, unless otherwise specified;
- For continuous endpoints, the summary statistics will include mean, standard deviation, median, and range (minimum and maximum);
- For time-to-event endpoints, the summary statistics will include median time to event-free survival, 25th and 75th percentiles and number of patients at risk at specified time points;
- For categorical endpoints, the summary statistics will include counts and percentages;
- Confidence intervals, when presented, will generally be constructed at the 95% level. For binomial variables, exact methods will be employed unless otherwise specified.

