Week 13 Day 1	58	85	127
Week 25 Day 1	128	169	211
Week 37 Day 1	212	253	295
Week 49 Day 1	296	337	365
Safety Follow-up ^a	Date of last dose + 2 days in relugolix arm Date of last dose + 8 days in leuprolide arm	Date of last dose + 30 days	Date of last dose + 45 (59 ^c) days
60-Day Testosterone Recovery ^b	Date of last dose + 46 days	Date of last dose + 60 days	Date of last dose + 75 days
90-Day Testosterone Recovery ^b	Date of last dose + 76 days	Date of last dose + 90 days	Date of last dose + 119 days

Date of last dose in leuprolide acetate ends 12 weeks after the last leuprolide acetate injection.

^a The safety follow-up visit window will be restricted to assessments prior to the date of initiation of another investigational agent or hormonal therapy or surgical intervention, whichever occurs first.

^b Approximately 100 patients receiving relugolix and 50 patients receiving leuprolide acetate who complete the 48 weeks of study treatment and, in the opinion of the investigator, can remain off androgen deprivation therapy for 90 days will be included in the testosterone recovery 60- and 90-day follow-up visits.

^c For patients not enrolled in the testosterone recovery follow-up, the end day of safety follow-up visit can be extended to day 59 after the date of last dose.

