4.4.1. By -Visit Endpoints

By-visit endpoints will be analyzed using observed data, unless otherwise specified. For observed data analyses, missing data will not be imputed and only the observed records will be included.

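### The EQ-5D-5L improvement table divides the 60- and 90-day recovery visits by all patients with a baseline answer, which caps those percentages near 16% in both arms

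*SAP*

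**What the plan says.** For each of the five EQ-5D-5L dimensions, SAP section 7.6.2 states that "the count and proportion of improvement by level or at least one level will be tabulated by treatment group and each visit". The next sentence sets the denominator: "The denominator for the proportion will be based on the number of patients who provided non-missing responses to the dimensions at baseline". It asks for no answer at the visit being tabulated and makes no exception for any visit.

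Section 7.6 schedules the questionnaires at Day 1, Weeks 5, 13, 25, 37 and 49, and the 30-day safety follow-up. It then adds: "They are also completed in the 60-day and 90-day testosterone recovery follow up if patients are participating in the testosterone recovery follow up". Table 3 in section 4.3.6 lists the 60- and 90-day visits among the quality-of-life analysis windows. Its footnote limits them to "Approximately 100 patients receiving relugolix and 50 patients receiving leuprolide acetate who complete the 48 weeks of study treatment" and who can, in the investigator's opinion, stay off androgen deprivation for 90 days.

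The general conventions differ from 7.6.2. For by-visit observed data, section 4.1 says that "calculation of percentages will be calculated on the basis of the number of patients with non-missing data as the denominator, unless otherwise specified". For by-visit endpoints, section 4.4.1 says that "missing data will not be imputed and only the observed records will be included". Both rules allow exceptions specified elsewhere.

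**The concern.** A patient with a baseline answer and none at the visit stays in the denominator and cannot enter the numerator, so he counts as not improved. At visits that every patient is due to attend, this is a convention about missing data. At the 60- and 90-day visits it is something else: about five in six men are absent because the design never called them, and they are still counted as not improved.

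The time course after stopping treatment is what suffers. A reader following the table from Week 49 to the 90-day visit would see the improved percentage fall steeply in both arms, although nothing need have changed in the men who answered. The recovery visits are the only ones that show quality of life well after treatment ends, so the table would mislead there.

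**Working it through.** The SAP gives no EQ-5D-5L percentage, sample size or power, so there is no stated figure to reproduce. The check is a ratio of the patients who can answer at a visit to the patients in the stated denominator.

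**Inputs from the SAP**
- Arm sizes, section 2.2: "approximately 915 patients (610 receiving relugolix, 305 receiving leuprolide acetate".
- Recovery subset, section 4.3.6, Table 3 footnote: about 100 relugolix and 50 leuprolide.
- Planned dropout, section 2.2: 15%.
- Expected total enrolment through amendment 3, section 2.1: about 1100.

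**Assumptions, not in the SAP**
- Baseline completion of the questionnaire: 100%, varied down to 80%.
- Proportion of answering patients who improve: 30%, for illustration only.

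**Ceiling at 60 and 90 days** = subset size / (arm size × baseline completion)
- Relugolix, 100% completion: 100/610 = 16.4%.
- Leuprolide, 100% completion: 50/305 = 16.4%.
- Both arms together: 150/915 = 16.4%.

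| Baseline completion | Relugolix | Leuprolide | Ceiling |
|---|---|---|---|
| 95% | 100/579.5 | 50/289.75 | 17.3% |
| 90% | 100/549 | 50/274.5 | 18.2% |
| 80% | 100/488 | 50/244 | 20.5% |

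If the table is rerun on about 1100 patients with the same 150 in recovery follow-up, the ceiling is 150/1100 = 13.6%. Section 7.4.3.5 says that enrolment to that follow-up is already complete, so the numerator would not grow.

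**What would be reported if 30% of answering patients improve**
- 90 days, stated rule: 0.30 × 100/610 = 4.9% for relugolix and 0.30 × 50/305 = 4.9% for leuprolide.
- 90 days, denominator limited to recovery participants with a baseline answer, all of them responding: 30/100 = 30% and 15/50 = 30%.
- Week 49, stated rule, 15% missing: 0.85 × 0.30 = 25.5%.

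The apparent fall from 25.5% to 4.9% comes wholly from the denominator, because the improvement rate among those answering was held at 30% throughout.

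**The case against.** **No rule is broken.** Sections 4.1 and 4.4.1 both yield to anything specified elsewhere, and 7.6.2 does specify otherwise. This stands. A reader might infer that 7.6.2 contradicts the general conventions; it does not.

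**On treatment, counting missing as not improved is a recognised convention.** The SAP itself applies it to PSA response (7.4.3.3) and undetectable PSA (7.4.3.4). A complete-case denominator has its own bias: if sicker men leave, improvement seems to rise among those who remain. This also stands, so the rule should not be called wrong at every visit. One difference remains. The PSA sections say openly that patients without an assessment are nonresponders, whereas 7.6.2 leaves the reader to work it out.

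**No false treatment difference is shown.** A reader might infer that the denominator creates a spurious contrast between the open-label arms. With assumed dropout of 10% versus 20% and 30% improvement among responders in both arms, the table would read 0.90 × 30% = 27% against 0.80 × 30% = 24%. But the SAP gives a single 15% dropout rate and no sign of imbalance, so that contrast rests on the assumption alone. At the recovery visits the planned subset keeps the 2:1 ratio and the ceiling is equal in both arms.

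**The endpoint is minor.** Table 1 places EQ-5D-5L among the secondary endpoints not for hierarchical testing and describes it as absolute values and changes. Section 7.4.2 names only the EORTC instruments, and 7.6.2 plans no test of this proportion. This stands and limits the weight of the point.

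**A milder reading is possible.** The denominator sentence may mean only that a baseline answer is needed to judge improvement. Table 1 qualifies follow-up reporting with where applicable, and a programmer might restrict the recovery columns unprompted. Counts would also be printed beside the percentages. But no sentence requires the restriction, and wording that can yield either 4.9% or 30% from the same data needs settling.

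**Conclusion.** The point holds for the 60- and 90-day columns. As written, the rule includes men never scheduled for those visits and caps the improved percentage at about 16% in each arm. The exact ceiling depends on two quantities: baseline completion, which the SAP does not give, and the total in the denominator. Across the values tried it runs from 13.6% to 20.5%, so about 16% is the central figure and not a fixed limit. The consequence is a misleading level and time course after treatment. It is not a bias between arms, and it touches no alpha-protected result.

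For on-treatment visits the plan's choice is a defensible trade-off that needs a label and a companion figure, not replacement.

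**What to change.** Amend the denominator sentence in section 7.6.2 in two parts.

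1. **60- and 90-day visits:** use as denominator the testosterone-recovery participants with a non-missing baseline response to the dimension, and print that n in the column.
2. **On-treatment visits:** keep the baseline denominator and state that a missing response counts as not improved. Beside it, show the number responding and the observed-case proportion, based on patients with non-missing responses at both baseline and the visit, as in section 4.1.

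The cost is a few lines of SAP text and a change to one table shell; no new data are needed. The downside is a denominator that varies by visit. The recovery columns also describe a selected group of treatment completers, so a footnote should say that they are not directly comparable with Week 49.

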8. PHARMACODYNAMIC ANALYSES

Predose concentrations and change from baseline at each visit will be summarized in predose concentrations of luteinizing hormone (LH), follicle-stimulating hormone (FSH), dihydrotestosterone, and sex hormone-binding globulin. FSH concentration level at Week 25 Day 1 between relugolix and leuprolide acetate will be compared using the two-sample t-test.

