2. STUDY DESIGN

2.1. Summary

The MVT-601-3201 (HERO) study is a phase 3, multinational, randomized, open-label, parallel-group study to evaluate the safety and efficacy of relugolix in patients with androgen-sensitive advanced prostate cancer who require at least 1 year of continuous androgen deprivation therapy. Oral relugolix or leuprolide acetate depot subcutaneous or intramuscular injection will be administered to patients with prostate cancer who require androgen deprivation therapy. The primary endpoint is sustained castration rate, defined as the cumulative probability of testosterone suppression to < 50 ng/dL (1.7 nmol/L) while on study treatment from Week 5 Day 1 (Study Day 29) through Week 49 Day 1 (Study Day 337).

Approximately 915 patients will be enrolled and randomized in a 2:1 ratio to the following two treatment groups:

- Oral relugolix 120 mg once daily, following a loading dose of 360 mg on Day 1;
- Leuprolide acetate 22.5 mg (or 11.25 mg in some Asian countries) every 3 months (3-M) depot subcutaneous or intramuscular injection.

Randomization will be stratified as follows:

- Geographic region: North and South America; Europe; Asia and Rest of World;
- Presence of metastatic disease: yes, no;
- Baseline age: ≤ 75 years old, > 75 years old.

After the initial 915 patients have been enrolled under protocol amendment 2, only patients with metastatic advanced prostate cancer will be enrolled under protocol amendment 3 to assess castration resistance free survival (ie, time to castration resistance) as a key secondary endpoint. A total of approximately 390 patients with metastatic disease as the high-risk subgroup for developing castration resistance, randomized in a 2:1 ratio to relugolix versus leuprolide acetate, are required to evaluate castration resistance free survival. In parallel, for approval in China 138 patients in China and Taiwan will be enrolled, with or without metastatic advanced prostate cancer, under protocol amendment 3. To support applications across various countries and regions, a total of approximately 1100 patients is expected to be enrolled in the study.

[figure not shown]

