7. EFFICACY ANALYSES

7.1. General Considerations

Unless otherwise specified, efficacy analyses will be conducted using the mITT population according to the randomized treatment assignment and will be stratified by the randomization stratification factors (geographic region, presence of metastatic disease, and baseline age). If the group of patients from any of the individual randomization stratification factors (eg, with presence of metastatic disease) comprises < 10% of the entire mITT population, this stratification factor will be collapsed for stratified analyses. In addition, if there were < 15 patients in one of the 12 strata, stratification factors of presence of metastatic disease and baseline age would be used in the stratified analysis for more robust strata-adjusted estimation of treatment effect. If there is a discrepancy > 5% between interactive web response systems (IWRS) and CRF on a stratification factor, the stratification factor reported in CRF will be used as primary analyses and that reported in IWRS will be used as sensitivity analyses, unless otherwise specified. In the case of a discrepancy > 5% between IWRS and CRF on the presence of metastatic disease stratification factor, patients with metastatic prostate cancer will be identified from CRF instead of from IWRS.

For efficacy endpoints related to testosterone test results, analytical testosterone results from the central bioanalytical laboratory using a liquid chromatography–tandem mass spectrometry method, with a lower limit of quantification of 5 ng/dL, will be used. Unless the endpoints are related to testosterone recovery, results from safety follow-up, 60-day and 90-day testosterone recovery (refer to [Table 2](#)) will be excluded from the efficacy analyses.

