7.2. Multiplicity Adjustment

The primary and the key secondary efficacy analyses will be performed at an overall two-sided type I error of 0.05. A test will be deemed statistically significant if the two-sided p-value rounded to 4 decimal places is less than 0.05. If the result of the primary endpoint analysis meets the respective evaluation criterion of the primary endpoint, the key secondary endpoints will then be tested with a fixed-sequence testing procedure (as illustrated in [Figure 2](#)) to maintain the overall familywise error rate of 0.05 for the testing of primary and key secondary endpoints.

The key secondary endpoints with alpha protection for labelling purposes are identified and defined in [Section 7.4.1](#).

All p-values (if provided) aside from the endpoints listed in the testing order are not adjusted in multiplicity, thus are at a nominal level of 0.05.

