7.4. Secondary Efficacy Endpoints

7.4.1. Key Secondary Efficacy Endpoints with Alpha-Protection

The key secondary endpoints will be tested in the following order (see [Figure 2](#)) for different regulatory agencies, with a fixed-sequence testing procedure to control the overall familywise error rate at a two-sided type I error rate of 0.05 across primary and key secondary endpoints.

[figure not shown]
For the testing order to be submitted to the FDA, Evaluation Criterion 2 for noninferiority of the primary efficacy endpoint will be assessed first in the order of hierarchical hypothesis testing for the key secondary endpoints after Evaluation Criterion 1 is met.

For the testing order to be submitted to EMA and PMDA, Evaluation Criterion 2 for noninferiority of the primary efficacy endpoint will be the primary efficacy assessment.

Timing of analyses for primary and key secondary endpoints is also included in [Table 4](#).

Castration resistance free survival and time to testosterone recovery back to 280 ng/dL at 90-day follow-up will be tested at the final analysis only if all the above endpoints reach statistical significance in the primary analysis. Endpoints in the higher order will be updated with descriptive statistics in the final analysis.

Figure 2: Diagram of Testing Order in Primary and Key Secondary Endpoints for Different Regulatory Agencies

Abbreviations: CI = confidence interval; EMA = European Medicines Agency; PC = prostate cancer; US FDA = United States Food and Drug Administration; PMDA = Japanese Pharmaceutical and Medical Device Agency.

Table 4: Testing Order and Timing of Analysis for Primary and Key Secondary Endpoints for Different Regulatory Agencies

Endpoints	Testing Order for the US FDA		Testing Order for EMA and PMDA	
	At Primary Analysis	At Final Analysis	At Primary Analysis	At Final Analysis
Sustained castration rate per Evaluation Criterion 1 ($\geq 90\%$ in relugolix)	1	Update	NA	Update
Sustained castration rate per Evaluation Criterion 2 (noninferiority of relugolix compared with leuprolide acetate)	2	Update	1	Update
Castration rate on Week 1 Day 4	3	Update	2	Update
Castration rate on Week 3 Day 1	4	Update	3	Update
Confirmed PSA response rate at Week 3 Day 1	5	Update	4	Update
Profound castration rate at Week 3 Day 1	6	Update	5	Update
FSH level at Week 25 Day 1	7	Update	6	Update
Castration resistance free survival during the 48-week treatment in patients with metastatic prostate cancer ^a	NA	8	NA	7

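### The alpha-protected FSH comparison at Week 25 is an unadjusted t-test with no stated variance form; it gives up precision, and under 2:1 allocation its size is not fixed

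*SAP*

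**What the plan says.** SAP Table 4 (Section 7.4.1) lists "FSH level at Week 25 Day 1" at position 7 in the FDA testing order and position 6 in the EMA/PMDA order. Castration resistance free survival and testosterone recovery rank below it and are tested only if every endpoint above them is significant. Section 7.2 sets the error rate: "The primary and the key secondary efficacy analyses will be performed at an overall two-sided type I error of 0.05".

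The test itself appears only in Section 8: "FSH concentration level at Week 25 Day 1 between relugolix and leuprolide acetate will be compared using the two-sample t-test". That section also has change from baseline in FSH summarised at each visit, so baseline FSH is available, but no test uses it. No covariate, stratification, transformation or variance form is given.

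Two other places show how the SAP treats comparable analyses. Section 7.1 says that, where nothing else is specified, efficacy analyses "will be stratified by the randomization stratification factors (geographic region, presence of metastatic disease, and baseline age". Section 7.6.1, on quality-of-life scales outside the testing hierarchy, says that "a mixed model using repeated measures will be performed with baseline scores, treatment, visit, randomization stratification factors" and a treatment-by-visit interaction.

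On allocation, Section 2.1 says: "Approximately 915 patients will be enrolled and randomized in a 2:1 ratio to the following two treatment groups". Section 2.2 puts the arms at 610 and 305 and assumes 15% dropout. The SAP gives no effect size, SD or power for FSH.

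**The concern.** There are two separate issues.

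**Precision.** A pre-treatment value of the same hormone usually explains part of the variation in the on-treatment value. A comparison of Week 25 levels that ignores it has a larger standard error than it needs. FSH is a step in a fixed sequence, so a miss here also closes the route to castration resistance free survival and testosterone recovery. The quality-of-life scales, which carry no alpha, are adjusted for baseline and strata; this continuous endpoint, which does carry alpha, is not.

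**Size of the test.** An unqualified two-sample t-test can be run with a pooled variance or with separate variances (Welch). With equal arms and large samples the choice hardly matters. With 2:1 allocation it does: the pooled variance is weighted towards the larger relugolix arm, while the true variance of the difference is driven more by the smaller leuprolide arm. If the SDs differ, the pooled standard error is wrong, in a direction that depends on which arm is more variable. The SAP promises two-sided 0.05 for this step but does not name a form that delivers it under unequal variances.

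**Working it through.** **Inputs from the SAP.** Two-sided alpha 0.05 (Section 7.2); 2:1 allocation (Section 2.1); 610 and 305 patients and 15% dropout (Section 2.2). If all dropout fell before Week 25 (an assumption), about 610 × 0.85 ≈ 519 and 305 × 0.85 ≈ 259 patients would have data.

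**Assumed inputs, shown as ranges.** The SD ratio leuprolide/relugolix, and the within-arm correlation ρ between baseline and Week 25 FSH.

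**1. Size of the pooled test.** Let k be the variance ratio leuprolide/relugolix, s² the relugolix variance, and n and 2n the arm sizes.

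- True variance of the difference: s²/(2n) + k·s²/n = s²(1 + 2k)/(2n).
- Pooled estimate, large sample: s²·(2 + k)/3 × 3/(2n) = s²(2 + k)/(2n).
- True/pooled ratio: R = (1 + 2k)/(2 + k).
- Two-sided size: 2 × [1 − Φ(1.96/√R)].

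The SAP's own figure first: equal SDs give k = 1, R = 1 and size 0.050, so the stated 0.05 is reproduced.

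| SD ratio L/R | k | R | 1.96/√R | Size |
|---|---|---|---|---|
| 0.5 | 0.25 | 1.5/2.25 = 0.667 | 2.40 | 0.016 |
| 1 | 1 | 1 | 1.96 | 0.050 |
| 1.5 | 2.25 | 5.5/4.25 = 1.294 | 1.72 | 0.085 |
| 2 | 4 | 9/6 = 1.5 | 1.60 | 0.110 |

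The results are virtually the same at 519/259 as at 610/305.

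**2. Simulation check** (519/259, 20,000 runs, normal data):

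| SD ratio L/R | Pooled | Welch |
|---|---|---|
| 0.5 | 0.017 | 0.050 |
| 1 | 0.052 | 0.051 |
| 1.5 | 0.084 | 0.049 |
| 2 | 0.111 | 0.051 |

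With lognormal data of equal mean, Welch gave 0.048 to 0.051 in four of five settings. It gave 0.061 in the fifth, which combined strong skew with an SD ratio of 2.46; the pooled form gave 0.129 there.

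**3. Precision from baseline adjustment.** ANCOVA multiplies the residual variance by 1 − ρ². Take a difference that the unadjusted test detects with 80% power at 610/305: (1.960 + 0.842) × √(1/610 + 1/305) = 2.802 × 0.0701 = 0.196 SD. Adjusted power is Φ(2.802/√(1 − ρ²) − 1.960).

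| ρ | 1 − ρ² | Argument of Φ | Power |
|---|---|---|---|
| 0.3 | 0.91 | 2.937 − 1.960 = 0.977 | 84% |
| 0.5 | 0.75 | 3.235 − 1.960 = 1.275 | 90% |
| 0.7 | 0.51 | 3.923 − 1.960 = 1.963 | 98% |

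Any further gain from the randomisation factors is not quantified.

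**The case against.** A prespecified simple test on several hundred patients is defensible. Under randomisation, omitting baseline and strata does not bias the comparison or inflate type I error. Section 7.1 applies its stratification rule only where nothing else is specified, and Section 8 specifies something else. Other key secondary tests are unstratified too: testosterone recovery (Section 7.4.3.5) and castration resistance free survival in metastatic patients (Section 7.4.3.7). All of this stands. A reader might infer that Section 8 contradicts Section 7.1; it does not.

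A reader might also infer that the planned test has inflated type I error whenever variances differ. The SAP does not support that. Inflation needs both the pooled form, which is not named, and a larger SD in the smaller leuprolide arm, for which no figure is given. The opposite pattern makes the pooled test conservative. Welch is also a two-sample t-test.

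Finally, skewed hormone levels might suggest a large loss of power on the raw scale. With log-SD 1.0, correlation 0.5 and 20% lower FSH (all assumed, 560 versus 280 patients), simulated power is about 65% for the raw t-test against 94% for a log-scale ANCOVA. At log-SD 0.7 it is about 96% against more than 99%, and at 0.5 both are near 100%. The SAP gives no log-SD, so the large loss cannot be asserted.

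What the objection leaves standing is the unused baseline and the unnamed variance form.

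**Conclusion.** The point holds as a matter of efficiency and incomplete specification; it is not a demonstrated error-rate failure. An endpoint that carries alpha and gates others is tested without a baseline value that the SAP already has. The cost is precision: residual variance could fall to 91%, 75% or 51% of its unadjusted value at assumed correlations of 0.3, 0.5 or 0.7.

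The variance form is left open in a 2:1 design. If pooled, the true size runs from about 1.6% to 11% over assumed SD ratios of 0.5 to 2, and the SAP does not show which side of 5% applies. Welch removes nearly all of that dependence. Every figure here except the nominal 5% rests on SD ratios or correlations that the SAP does not supply. The primary endpoint is unaffected.

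**What to change.** In Section 8, replace the t-test sentence with a prespecified ANCOVA. The dependent variable is FSH at Week 25 Day 1. The terms are treatment, baseline FSH and the randomisation factors, using the collapsing and IWRS/CRF rules of Section 7.1. Standard errors are heteroscedasticity-robust (Welch-type), and the adjusted mean difference is reported with a two-sided 95% CI and p-value. State how patients without a baseline FSH value are handled. If the t-test is kept, name the unequal-variance (Welch) form.

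A log-scale analysis reported as a geometric mean ratio is optional. It would deal better with strong skew, but it changes the summary measure of an alpha-protected endpoint from a difference in means to a ratio, so it should be a deliberate choice.

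The recommended change needs no new data and keeps a mean difference as the effect measure. The cost is an SAP revision and revised programming, dated before database lock for the primary analysis. After lock, the adjusted analysis could only be supportive.
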